### Objective

Research studies in stuttering have shown that activity patterns in certain brain areas differ in people who stutter compared to people who do not stutter when speaking. The purpose of our study is to investigate how mild, non-invasive brain stimulation applied consecutively for five days affects speech relevant brain areas, which may in turn affect speech fluency and speaking-related brain activity in people who stutter. The long-term goal of this study is to test the therapeutic potential of transcranial direct current stimulation (tDCS) for the treatment of stuttering.

### 1. Specific Aims

- 1.1. Specific Aim #1: Determine effects of anodal HD-tDCS targeting left pSTG on speech fluency in adults who stutter.** Pre-training measures of stuttering severity (e.g., percent stuttering-like disfluencies, OASES scores) will be compared with those same measures immediately following training, as well as 4 weeks post-training. We hypothesize that when paired with a fluency-inducing speech condition, active stimulation targeting left pSTG will lead to a greater increase in speech fluency compared to behavioral training alone (sham stimulation).
- 1.2. Specific Aim #2: Determine effects of anodal HD-tDCS targeting left pSTG on performance on rhythm judgement tasks.** Pre-training measures of performance (reaction time and accuracy) on finger-tapping tasks and rhythm judgment tasks will be compared with those same measures immediately following training, as well as 4 weeks post-training. We hypothesize that when paired with a fluency-inducing speech condition, active stimulation targeting left pSTG will lead to a greater increase in performance on these tasks compared to behavioral training alone (sham stimulation).
- 1.3. Specific Aim #3: Determine effects of anodal HD-tDCS targeting left pSTG on functional connectivity within BGTC regions during speech production.** Pre-training measures of functional connectivity within BGTC regions will be compared before and immediately following training, as well as 4 weeks post-training. We hypothesize that when paired with intensive training under fluency inducing conditions, active stimulation targeting left pSTG will lead to increased functional connectivity within the BGTC network compared to behavioral training alone (sham stimulation).

### 2. Significance & Background

Developmental stuttering is a disorder of speech fluency affecting approximately 5% of preschool-age children. Up to 20% of these children continue to stutter well into adulthood (Yairi & Ambrose, 2013). Conventional treatments aim to improve fluency through behavioral strategies such as slow rate, prolonged speech, and easy onsets (Bloodstein & Ratner, 2008). A considerable amount of time and effort (> 100 hours) is needed to significantly improve fluency

(Andrews, et al., 1980), and over 70% of those treated experience relapse, particularly adults (Craig & Hancock, 1995; Craig, et al., 1996; Hancock et al., 1998). Success with delayed feedback is variable and short-lived (Foundas et al., 2013), and pharmacological treatments are largely ineffective and associated with side effects (Bothe et al., 2006; Maguire et al., 2010). Given that AWS often experience emotional, social, and vocational difficulties throughout their lives, there is a critical need for developing therapeutic interventions that result in long-term enhancement of speech fluency in people who stutter. There is accumulating evidence of subtle neural differences in people who stutter, and that the use of non-invasive brain stimulation improves motor and language performance. We propose to test if pairing stimulation with training will lead to effective, longer lasting increases in speech fluency and brain connectivity within related neural networks in AWS, beyond that of speech training alone (i.e., sham stimulation).

## 2.1. Applying an established theoretical framework and empirical data from neuroimaging to guide novel intervention research in stuttering.

Motivated by a neurobiologically plausible model of speech production (Gradient Order Directions into Velocities of Articulators [GODIVA]; Bohland et al., 2010) research suggest that stuttering may stem from disruption in the basal ganglia thalamocortical (BGTC) network, specifically in the connections among the basal ganglia (BG), supplementary motor area ([SMA]) and ventral premotor cortex ([vPMC]; Civier et al., 2013; Fig 1.). The disruption in the BGTC network affects coordination of precisely-timed movement initiation (subserved by SMA), activation of speech sounds (subserved by vPMC), and sequencing of sounds (subserved by BG), considered required to produce fluent speech. The SMA is considered critical in planning over-learned, complex movement routines, including speech production, that are *internally timed and initiated*, rather than in response to external cues (Cunnington et al., 1996; Packman et al., 2007). One interpretation is that SMA assists with coordinating the timing of speech movements through connections with the motor system (Bohland & Guenther, 2006). GODIVA hypothesizes that stuttering is a result of delayed activation of the upcoming syllable's motor plan. Indeed, people who stutter demonstrate difficulty in preparing and controlling precisely-timed complex movements, including initiation of propositional speech (Packman & Onslow, 2002). Further, both AWS and CWS demonstrate poor performance on non-speech tasks that involve timing and rhythm (Wieland et al. 2015a, 2015b, 2016; Chang et al. 2016) and attenuated functional connectivity among BGTC network regions (Chang & Zhu, 2013, Lu et al., 2009; 2010).

## 2.2. Effects of fluency-inducing conditions on behavioral and brain measures.

If the overt disfluencies in stuttering are reflective of disrupted connectivity within BGTC network regions, there is at least some evidence that the application of *external* timing cues can significantly decrease stuttering (i.e., increase fluency) by acting on this 'timing network'. Most speakers who stutter exhibit temporarily increased fluency during conditions that include an *external* pacing element, such as choral speech or with a metronome (Park & Logan, 2015). Such techniques are also associated with more 'normalized' brain activation patterns (i.e., similar to activation patterns found in nonstuttering speakers), such as increased left frontotemporal activation, and reduced motor activation, including right frontal opercular areas, as well as increased pSTG (De Nil et al., 2003; Giraud et al., 2008; Kell et al., 2009; Neumann et al., 2005; Toyomura et al., 2011; 2015). Giraud et al. (2008) found that activity in the basal ganglia was correlated with stuttering severity before, but not after, 3 weeks of speech fluency training. This suggests that therapy can modulate brain activity in regions within the proposed 'timing network' focused on in this proposal. If, at its core, stuttering reflects an internal timing deficit that impacts the precise initiation of speech movements leading to overt disfluencies, this would suggest that the BGTC circuits, including SMA-putamen and pSTG, are functionally

[figure not shown]

Figure 1. a. Basal ganglia thalamocortical network (BGTC) structures in red. b. Motor subsystem in GODIVA model releases planned speech movements (both cortical and subcortical areas). Speech sound map in ventral premotor cortex (vPMC) provides input regarding sensorimotor programs to putamen, involved in sequencing motor movements. The initiation map in SMA aids in initiation of movement for speech production, and is structurally connected with putamen.

aberrant in stuttering. Therefore, we aim to augment improvements in fluency through the modulation of functional connectivity within BGTC by pairing noninvasive brain stimulation to pSTG with an induced fluency condition, as increases in activation in pSTG have been shown to support improved speech fluency.

**2.3. Potential impact of neuromodulation approaches on improving stuttering treatment.** Despite recent advancements in our understanding of the neurobiology of stuttering, *neuroscience-based treatments* for stuttering are limited. Techniques that exploit the principles of neuroplasticity, such as neuromodulation with transcranial direct current stimulation (tDCS), may offer new insight into effective stuttering treatment. This technique is safe, well-tolerated, and non-invasive (Bikson et al., 2016) compared to other stimulation techniques like transcranial magnetic stimulation (TMS). Additionally, tDCS readily lends itself to double-blinded, sham-controlled studies suitable for *randomized clinical trials* (Woods et al., 2016). Conventional tDCS sponge electrodes are large (e.g., 35 cm^2), resulting in diffuse current spread, but focality has recently been improved with high definition (HD) electrodes, which will be used in the proposed research (Datta et al., 2008; 2009; Kuo et al., 2013). Stimulation can increase or decrease brain activity using a weak constant electrical current (1-2mA). Unlike TMS, which can induce neural firing, tDCS affects resting membrane potential through the modulation of cellular-level changes, including sodium and calcium-dependent channels and NMDA receptor activity, promoting long-term potentiation/depression (LTP/LTD) like effects (Bolognini et al., 2011; Fritsch et al., 2010; Stagg et al., 2011). Previous findings suggest this is especially true when stimulation is delivered over multiple rather than single sessions (Woods et al., 2016), as will be done in the proposed intensive training program.

Both cognitive and motor rehabilitation fields have benefitted from the *translational nature of tDCS*. It can introduce functional improvement in language and motor skill learning (Cappon et al., 2016; Hashemirada et al., 2016; Hartwigsen, 2015; Madhavan & Shah, 2012; Reis et al., 2009). Applying tDCS during motor training can induce short- and long-term (up to 3 months) effects on rehabilitation after stroke (Allman et al., 2016; Reis et al., 2009). Further, (HD)-tDCS improves performance in unimpaired speakers, and speakers with aphasia, on such tasks as verbal fluency, speech reaction time, naming, numerical processing, spelling, and learning an artificial grammar (Baker et al., 2010; Cattaneo et al. 2011; De Vries et al., 2010; Dockery et al., 2009; Fertonani et al., 2010; Fiori et al., 2011; Fridriksson et al., 2011; Iyer et al., 2005; Malyutina & Den Ouden, 2015; Richardson et al., 2015; Sparing et al., 2008; Vestito et al., 2014).

Another approach is to use tDCS in conjunction with functional magnetic resonance imaging (fMRI) to examine brain function before and after stimulation (Baudewig et al., 2001; Hampstead et al., 2014; Jang et al., 2009; Keeser et al., 2011; Polanía et al., 2012b; Stagg et al., 2009). Stimulation not only affects cortical areas immediately under the electrode(s), but also anatomically and functionally connected cortical (Holland et al., 2016; Pereira et al., 2013) and subcortical (Polanía et al., 2012a; Lang et al., 2005; Liew et al., 2014; Weber et al., 2014). Such findings are important precedents for the proposed project. By stimulating left pSTG during choral speech, we aim to increase functional connectivity within BGTC regions through cellular-level changes that underlie LTP effects supporting long-term fluency.

#### **2.4. Summary of significance**

Accumulating evidence supports the effectiveness of neuromodulation approaches in treating speech-language disorders, and converging evidence points to specific brain regions (e.g., pSTG) that may be targeted to increase fluency in stuttering speakers. The current proposal aims to determine whether neuromodulation targeting the left pSTG can contribute specifically to increases in speech fluency of AWS and/or changes in brain functional connectivity in a network of regions supporting internal timing of speech (i.e., the BGTC). Presently, there is evidence that when compared to fluent controls, people who stutter exhibit difficulties relevant to generating internal timing that supports speech motor control, difficulties that appear related to abnormalities within the BGTC. The proposed project is *significant* because it has the potential to lead to neuroscience-based treatments that may have longer-lasting positive outcomes, reducing negative impacts on the lives of people who stutter. The objective of the proposed project is to establish the degree to which traditional fluency-inducing techniques can be augmented through targeted stimulation of relevant brain areas. Such efforts must precede testing of any other

more practical, generalizable behavioral technique to be paired with (HD)-tDCS in treating stuttering.

### 3. Method

#### 3.1. Subject Recruitment and Screening

Participants will be recruited through community advertisements such as UMHSClinicalStudies.org or Craigslist, in the hospital, community, local papers; word of mouth; letters to area clinicians; stuttering support groups; through the National Stuttering Association website; and on lab websites and Facebook pages ([www.neurostutteringresearch.com](http://www.neurostutteringresearch.com), [www.facebook.com/msudevelopmentalstutteringproject/](http://www.facebook.com/msudevelopmentalstutteringproject/)). We also will post infrequently in other relevant Facebook groups. All potential participants who contact the study coordinator will be briefed on the study and screened to ensure eligibility criteria are met. If the criteria are met, a face-to-face interview will be arranged, during which the written consent form will be completed, and the full assessment will occur. Information about the study may also be exchanged via email but participants will be discouraged from communication any personal information via the email system. Participants will be contacted up to 3 times if no response is received following their initial contact with the research team.

**General participant criteria.** The following criteria must be met by all participants:

- Between the ages of 18 and 65 years
- A history of persistent developmental stuttering,
- Stuttering severity ranging from mild to very severe, specifically Stuttering Severity Instrument (SSI) total score of 20 or higher and/or stuttering rates of 3% or higher,
- Not received any treatment for stuttering within the past year,
- No other neurological conditions such as Tourette's syndrome or post-traumatic stress disorder,
- Not taking any medications/drugs that affect brain function.
- No history of serious medical or neurological illness such as epilepsy and Parkinson's disease,
- No history of closed head injury (e.g., concussion),
- No history of reading disorders,
- No hearing loss,
- Not taking any medication, prescription or non-prescription with any psychotropic effects at the time of the study,
- No metal or electronic implants such as cochlear implants, and pacemakers,
- Scores within 1SD of the norm on the standardized tests for the study.

**3.2. Assessment.** Prior to assessment, the study will be explained to participants and an informed consent document signed. The assessment will consist of 3 parts: 1) Interview (review of medical history and history of stuttering), 2) standardized tests, and 3) speech sample collection.

**3.3. Interview.** Participants will be interviewed to obtain information on their medical and general speech history, as well as family history of stuttering, stuttering onset, and development. We will also ask questions about their musical training experience.

**3.4. Standardized assessments.** The standardized tests will provide measures of expressive and receptive language/vocabulary, speech fluency/stuttering severity, and working memory. The assessments may consist of the following:

- The Peabody Picture Vocabulary Test ([PPVT-3; Dunn & Dunn, 1997](#))
- Expressive Vocabulary Test ([EVT-3; Williams, 1997](#))
- Overall Assessment of the Speaker's Experience of Stuttering (Yaruss & Quesal, 2010)
- Operation span (Unsworth, Heitz, Schrock, & Engle, 2005)

**3.5. Speech samples.** Speech samples will consist of a reading task and a conversation between the participant and researcher. The reading and conversation will be audio- and video-taped. Speech samples will be transcribed off-

line and analyzed for disfluencies and any unusual speech-language usage. The severity of stuttering will be based on the reading and conversation speech samples collected. The Stuttering Severity Instrument (SSI-4) ([Riley, 2009](#)), will be used to assess the severity of stuttering during these samples. Two trained speech pathologists or research investigators experienced in disfluency analysis will independently score the SSI form to establish reliability of measurement. To be identified as a person who stutters, the overall SSI score is required to be 20 (corresponding to mild stuttering severity) or greater. Additionally, participants will be asked to rate their speech (e.g., very fluent, disfluent) and stuttering (e.g., mild, severe) within and outside the research setting.

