### **3.6. Experimental design**

Participation will require 10 separate visits.

- Visit 1 will consist of the interview, speech/language assessments, and a baseline speech sample (~ 1.5 hours).
- Visit 2 will consist of a second baseline speech sample and behavioral testing (~ 2 hours).
- Visit 3 will consist of a third baseline speech sample, MRI, and the first tDCS session (~2 hours).
- Visits 4, 5, 6 will consist of tDCS sessions (~1 hour each; 3 hours total)
- Visit 7 will consist of the final tDCS session, MRI, and behavioral testing (~3.5 hours)
- Visits 8-9 will consist of the second and third post-testing speech sample (~15 minutes each; 30 minutes total)
- Visit 10 will be 1 month (~4 weeks) after visit 7 and will consist of a final speech sample, MRI, and behavioral testing (~3.5 hours)

Visits 3 through 7 must be completed on consecutive days. Participants will also be sent a short online survey about their experiences with the tDCS procedure about 2 days after each visit; this survey will take no more than 5 minutes to complete. The potential amount of time needed for the entire study will be approximately 15-17 hours.

This project employs a between-subjects, sham-controlled, double-blinded design. Participants will be randomly assigned to either active or sham stimulation conditions. Total study time will be 2 weeks, plus a follow up appointment 4 weeks after training ends. Three speech samples (SS) will be collected during the first 1-2 weeks prior to training to obtain average baseline measures of speech fluency. Speech-language (SL) testing and collection of the first speech sample will be during the first visit. Visit 2 will consist of the second baseline speech measure and baseline measures of behavioral performance on the rhythm judgment tasks. On the third baseline visit, designated as Time 1 for analyses in sections 2 and 3 below, pre-training fMRI scans will be acquired and the first HD-tDCS session will be completed. Visits 4-6 will consist of tDCS sessions only. Visit 7 will consist of the final tDCS session, post-training MRI, and post-training behavioral testing and speech sample. Within the next 1-2 weeks, two speech samples (visits 8, 9) will be collected. Visit 10 will be 4 weeks after visit 7 and will consist of the final speech sample, fMRI, and behavioral testing.

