#### **Primary Outcome Measure 2 - Change in percentage of stuttered syllables produced during speech sample (speech fluency)**

To measure effects of tDCS on fluency we will calculate %SLD at each of the 3 time points. Two speech pathologists trained in disfluency analysis and blinded to group assignment and time point will independently score %SLD to establish reliability. The outcome measure is the difference between baseline measures of (mean) %SLD and the same measure at 2 post-training time points. While an increase is expected to occur in both groups, we expect that the magnitude of any differences will be greater in the group receiving active stimulation compared to training alone (sham stimulation). We expect that: 1) %SLD will decrease significantly more in the active stimulation group compared to the sham group, and 2) these differences will be maintained when assessed 4 weeks later.

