## **4. Protection of Human Subjects**

### **4.1. Risks to Human Subjects**

#### **Human Subjects Involvement, Characteristics, and Design**

The proposed study will involve healthy adult participants between 18-65 years of age. All participants in the tDCS arm will be those who have been diagnosed with developmental stuttering. Although women are underrepresented in samples of adults with stuttering, we will make every effort to include women in the proportion they occur in the population with this disorder. While the ratio is closer in childhood, approximately 3 males to 1 female, in adults the ratio is approximately 5 males to 1 female. We will gather information on each participant's medical, social, and developmental history, and speech, language, and hearing background. In addition, stuttering participants will be audio-video recorded to obtain speech samples during conversation and reading. These will be used to determine their stuttering severity level using the standardized assessment, stuttering severity instrument (SSI-4; Riley 2009). Two trained speech-language pathologists experienced in disfluency analysis will independently score the SSI form to establish reliability of measurement. Participants will be randomly assigned to one of the two groups (active vs. sham stimulation).

In order to reach our target of 24 eligible adults who stutter who complete the study, and 50 eligible controls to participate in the rhythm tasks sub study only (see section 4.5 below), we will consent up to 200 people during the oral phone screening. It is possible that some participants who pass this screening may still become ineligible during the first visit, for example due to scoring below normal on the standardized tests, or having a stuttering score that is too low.

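### Primary fluency outcome is an unadjusted difference in %SLD over an uncapped severity range; if change or noise scales with severity, this costs power, and baseline adjustment recovers part of it

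*Combined protocol and SAP*

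**What the plan says.** Protocol section 3.10, Primary Outcome Measure 2, states: "The outcome measure is the difference between baseline measures of (mean) %SLD and the same measure at 2 post-training time points". It names no test, model, covariate, transformation or significance level. Section 1.1 describes the same before-and-after comparison: "Pre-training measures of stuttering severity (e.g., percent stuttering-like disfluencies, OASES scores) will be compared with those same measures immediately following training".

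On severity, section 3.1 admits "Stuttering severity ranging from mild to very severe, specifically Stuttering Severity Instrument (SSI) total score of 20 or higher", followed by "and/or stuttering rates of 3% or higher". Neither limb has an upper bound, and the wording of the second means that 3% is not a firm floor. Section 3.5 gives a different rule, with no 3% alternative: "the overall SSI score is required to be 20 (corresponding to mild stuttering severity) or greater".

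On size and design, section 4.1 says: "In order to reach our target of 24 eligible adults who stutter who complete the study". Section 3.6 says: "Participants will be randomly assigned to either active or sham stimulation conditions". It gives no ratio and no stratification by severity. It also collects three pre-training speech samples "to obtain average baseline measures of speech fluency".

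**The concern.** A percentage-point change does not mean the same thing across this range. Someone who enters at 3% can improve by at most 3 points, which is complete fluency. For someone who enters at 25%, 3 points is a small change. %SLD is also a rate built from counts, so at least its counting error rises with its level.

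If benefit, noise or both scale with severity, the spread of the change score is set largely by the most severe participants. With about 12 people per arm, the result for one of the two primary outcomes could then turn on a few of them, and a real proportional benefit would be easier to miss. Averaging three baseline samples reduces within-person noise but does not remove this scaling.

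**Working it through.** **Inputs.** From the documents: 24 completers, two arms, mild to very severe with no cap, outcome a difference in %SLD. Assumed, because the documents are silent: 12 per arm, two-sided 0.05, and every distribution, SD and effect size below. The plan gives no sample-size calculation, so there is no figure to reproduce. For reference, a two-sample t-test with 12 per arm has 80% power at a standardised difference of about 1.20, and 47% at 0.8.

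**Step 1: does noise depend on level?** Counting error for n syllables is √(p(1−p)/n). With an assumed n = 500:
- at 3%: √(0.03 × 0.97/500) = 0.76 points
- at 25%: √(0.25 × 0.75/500) = 1.94 points

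This component alone is not constant.

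**Step 2: weight of the three most severe.** Suppose three people are r times as severe as the other 21, and error variance is proportional to severity to the power k. Their share of the error variance is 3r^k/(3r^k + 21).
- Constant SD (k = 0): 3/24 = 12.5%.
- Variance proportional to baseline (k = 1), r = 3: 9/30 = 30%.
- SD proportional to baseline (k = 2), r = 2: 12/33 = 36%; r = 3: 27/48 = 56%; r = 4: 48/69 = 70%.

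With simulated log-normal baselines (median 5% or 7%, log-SD 0.4 to 1.0, with and without a 3% floor), the average share is 21-39% when variance is proportional to baseline. When the SD is proportional, it is 33-34% at log-SD 0.4, 53-58% at 0.8 and 57-65% at 1.0.

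**Step 3: power.** First model: baseline median 5%; sham reduction 0.2 on the log scale; further active reduction 0.4 (ratio e^−0.4 = 0.67); residual log-SD 0.34; 4,000 trials per row. The additive rows use an effect of 1.5 points and SD 1.25 points, both constant.

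| Scenario | Raw change, t-test | Baseline-adjusted points | Log, baseline-adjusted |
|---|---|---|---|
| Proportional, log-SD 0.4, 3% floor | 0.64 | 0.68 | 0.76 |
| Proportional, log-SD 0.8, 3% floor | 0.45 | 0.61 | 0.77 |
| Proportional, log-SD 0.8, no floor | 0.37 | 0.55 | 0.77 |
| Proportional, log-SD 1.0, no floor | 0.30 | 0.48 | 0.76 |
| Additive, log-SD 0.4, 3% floor | 0.80 | 0.78 | 0.62 |
| Additive, log-SD 0.8, 3% floor | 0.79 | 0.77 | 0.54 |

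Second model: three samples before and three after, 500 syllables each, %SLD falling 15% with sham and 45% with active, individual response log-SD 0.3. Power is 40-54% for raw change, 56-66% for baseline-adjusted points and about 72% on the log scale. Letting visit-to-visit log-SD run from 0.20 to 0.35, with baseline median 6-8% and log-SD 0.6-1.0, gives 33-53%, 48-66% and 62-75%. These figures apply to the time point just after training. The 4-week visit has a single speech sample, so power there is lower for all three methods.

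**Step 4: type I error.** In the first model under no effect, rejection rates are 0.037-0.042 (raw change), 0.045 (baseline-adjusted points) and 0.049-0.050 (log, baseline-adjusted). None is inflated.

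**Step 5: fragility of the log scale.** Give each participant in either arm a 5% chance of ending near 0.1% (baseline median 7%, log-SD 0.8, visit log-SD 0.25), and analyse log(%SLD + 0.1). Power is 37% on the log scale, 45% for baseline-adjusted points and 36% for raw change. With a 10% chance it is 22%, 37% and 29%.

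**The case against.** The strongest reply is that the plan is incomplete rather than wrong. Section 3.10 defines an outcome and names no model, so an adjusted or log-scale analysis is not excluded. Percentage points are a legitimate scale, type I error is sound, and if effect and noise are constant in points the raw scale is the better one. All of that stands. It argues for naming the model now, because an open choice could otherwise be made after the data are seen.

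Three stronger readings are tempting, and the documents do not support them.
- A reader might infer that about three of 24 people carry some 60% of the error variance. That share needs the top three to be about 3.2 times as severe as the rest with SD proportional to baseline, or 10.5 times with variance proportional. Simulations of the second model do show the three largest deviations making up 59-63% of the residual sum of squares. But those three are picked after the fact, the same share is 47% with equal normal errors, and they are not the three most severe people. The documents contain no %SLD distribution from which to settle the figure.
- A reader might infer that the test certainly loses power. The additive rows of the table show the opposite ordering.
- A reader might infer that the log scale should replace percentage points as the primary scale. Step 5 shows that a few near-fluent participants can make it weaker than simple baseline adjustment.

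**Conclusion.** The point holds conditionally. As written, the plan delivers an unadjusted percentage-point difference in a small trial with an uncapped severity range. If change or noise scales with severity, that choice is inefficient. In the proportional rows of the first model, baseline adjustment on the same scale raises power by 4 points (0.64 to 0.68) to 18 points (0.37 to 0.55), and the log scale adds more.

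Baseline adjustment is the safer part of the remedy. It beat the raw difference in every proportional and near-zero scenario, and in the additive rows it cost about 2 points of power (0.80 to 0.78, 0.79 to 0.77). The log scale is a trade-off.

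All power figures and variance shares rest on assumed distributions, effects and a 12-per-arm split, none of which is in the documents. The validity of the test is not in question.

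**What to change.** In section 3.10, under Primary Outcome Measure 2:
- State that arms will be compared at each post-training time point on %SLD, with mean baseline %SLD as a covariate, instead of on the raw difference. The estimated effect stays in percentage points. Using change as the dependent variable with the same covariate gives the identical arm comparison, so the outcome definition can remain.
- Prespecify one supportive analysis: log %SLD with log baseline %SLD as covariate, a constant for zero counts fixed now, reported as the active-to-sham ratio with a 95% interval.

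Sections 3.1 and 3.5 should also be reconciled on the entry rule, since the two versions imply different baseline spreads.

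The cost is a sentence or two and no new data, visits or participants. The covariate uses one degree of freedom and loses a little power if effect and noise are constant in points. The log analysis is sensitive to near-zero post-training values, which is why it is supportive only.

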#### **Secondary Outcome Measure 1 - Changes from baseline on the Overall Assessment of Speakers Experience of Stuttering (OASES)**

The OASES is a standardized assessment of the functional impact of stuttering on a person's life. There are 4 sub-tests: general information about speech, your reactions to stuttering, communication in daily situations, quality of life. Each one has a score from 1 to 5 with regard to impact (1 least, 5 most negative impact). These are combined to give a total impact score between 1 and 5, with 5 representing the highest negative impact on person's life. The change on the total impact score will be used.

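### Does the 1 SD entry rule on standardized tests also restrict OASES, the secondary outcome?

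*Combined protocol and SAP*

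**What the plan says.** The general participant criteria in section 3.1 apply to all participants. One reads "Scores within 1SD of the norm on the standardized tests for the study". It does not say which tests are meant, whose norm is used, or whether scores above the norm count as failures. The same list admits "Stuttering severity ranging from mild to very severe", with a floor on the SSI total (20) and/or on stuttering rate (3%) and no ceiling.

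Section 3.4 describes the tests: "The standardized tests will provide measures of expressive and receptive language/vocabulary, speech fluency/stuttering severity, and working memory". It then says "The assessments may consist of the following" and lists four instruments: PPVT, EVT, OASES and operation span. The SSI-4 is described separately, under speech samples in section 3.5.

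Section 3.10, Secondary Outcome Measure 1, states "The OASES is a standardized assessment of the functional impact of stuttering". The total impact score runs from 1 to 5, with 5 the worst, and "The change on the total impact score will be used". Specific Aim 1 also names OASES as a measure compared before and after training.

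Section 4.1 explains why some people who pass the phone screen may prove ineligible at the first visit, giving as examples "due to scoring below normal on the standardized tests, or having a stuttering score that is too low".

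**The concern.** Taken word for word, sections 3.1 and 3.4 together put OASES under a two-sided entry limit. OASES is the only stuttering-related instrument in the section 3.4 list, that section says the tests cover stuttering severity, and section 3.10 attaches the word standardized to OASES. A candidate more than 1 SD from an unnamed norm would then be turned away on the score that later serves as the secondary outcome. Candidates with the highest impact, who have the most room to improve on a 1 to 5 scale, would be among those lost. That would sit awkwardly with an entry list that sets no upper bound on stuttering severity.

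Section 4.1 appears to add a second difficulty, because it speaks only of scoring below normal. On OASES a low score means little impact, so a one-sided rule would remove the least affected people. Someone well above the norm would fail under section 3.1 and not under section 4.1. At stake would be the mix of people enrolled, the spread of the OASES outcome, and the number who must be screened to reach 24 completers.

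**Working it through.** **No figure in the plan to reproduce.** The documents give a target of 24 completing adults who stutter, without alpha, power, effect size, SD or dropout. They give no norm or SD for OASES. The question is first one of reading; arithmetic can only show what the literal reading would cost under assumptions.

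**Setting the passages side by side.**

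1. *Does the word standardized decide the scope?* Section 3.10 uses it for OASES. Section 4.1 uses it for the SSI-4. If the label alone brought an instrument under the 1 SD rule, the SSI would be caught too, yet section 3.1 already gives the SSI its own rule, a floor of 20 with no ceiling. The label cannot settle the matter.
2. *Does the section 3.4 list decide it?* The list is permissive ("The assessments may consist of the following"). It describes what the assessment may contain. It does not define the entry tests.
3. *What does section 4.1 show?* It names two grounds for failure, one on the standardized tests and one on a stuttering score that is too low. Listing them separately implies that the standardized tests in the entry rule are not the stuttering measures. That leaves vocabulary (PPVT, EVT) and working memory (operation span), for which a lower limit is the natural meaning.
4. *Do sections 3.1 and 4.1 set rival limits?* No. Section 4.1 offers an illustration in a paragraph about recruitment numbers and states no cut-off. Scoring below normal is one way of failing section 3.1, so the two are compatible. A pass rate for a section 4.1 rule cannot be calculated without supplying a cut-off that the section does not contain.

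**What the literal reading would cost, as illustration only.** Assume normal OASES scores with the norm's SD, and candidates averaging *d* SD above the norm.

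- Share passing: Φ(1 − d) − Φ(−1 − d).
- d = 0: 0.683 pass, so 31.7% fail, 15.9% in each tail.
- d = 1: 0.477 pass.
- d = 2: 0.157 pass.
- Baseline variance after restriction at d = 0: 1 − 2φ(1)/0.683 = 1 − 2 × 0.242/0.683 = 0.291. The SD ratio is √0.291 = 0.54.
- Otherwise eligible adults needed for 24 at d = 0, before dropout: 24/0.683 = 35.2, so 36, against 24 if OASES is exempt.

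The pass share runs from 68.3% down to 15.7% according to an assumed shift, and nothing in the documents fixes that shift. The 0.54 ratio, and the idea that only middle-impact adults would remain, hold only at d = 0. With an upward shift, the rule would instead keep the lower-impact part of the candidates.

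**Effect on the comparison.** The tests are given at visit 1 and stimulation starts at visit 3. A limit applied at entry acts on both randomized groups alike, so it cannot create a difference between active and sham.

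**The case for a change.** The best argument for a change is that eligibility text should not depend on inference. Section 3.1 names no exemption, section 3.4 mentions stuttering severity among the things the tests measure, and a literal-minded screener could apply the limit to OASES. The comparison with stuttering rate, which also serves as both entry criterion and outcome, is imperfect: that criterion is only a floor, whereas a two-sided OASES limit would also be a cap. Nor does the severity criterion strictly contradict such a cap, since OASES measures impact and severity is a different quantity.

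This much stands: the criterion leaves tests, norm and direction unstated, and naming them would cost only words. The direction is open for the vocabulary and memory tests as well, where the literal wording would exclude high scorers.

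The step from imprecise wording to a defect does not stand. No passage says that an OASES score makes anyone ineligible, and section 4.1 separates the two kinds of score. Using one instrument for entry and for outcome is no error in itself, and a baseline OASES is needed for a change score in any case. The visits at which OASES is given, and the time point that defines its change, are separate questions and lend no weight to this one.

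**Conclusion.** No change to the plan is needed. The 1 SD criterion is loosely worded, but the surrounding text leads staff to the sensible reading: a lower limit on the language and memory tests, with stuttering measures governed by their own criteria. Writing that down would alter no stated number, analysis or conclusion.

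This rests on two points. The first is that section 4.1's separation of the standardized tests from the stuttering score reflects how the rule is applied; no passage says so outright. The second is randomization, which keeps the active versus sham comparison unbiased even if the literal reading were followed. In that case the loss would be in recruitment yield, OASES range and generalizability. Its size cannot be determined from the documents: 31.7% excluded if scores are normal and centered on the norm, and more if candidates average above it.
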